### *Inclusion Criteria*

- Age  $\geq 18$  years
- Diagnosis of OAB-wet (OAB with urgency urinary incontinence) documented by clinical diagnosis
- Baseline  $\geq 1$  UUI episode/day averaged over a 3-day diary
- Is on a stable pharmacotherapy for OAB (antimuscarinic or  $\beta 3$ -agonist) for  $\geq 4$  weeks, with intent to remain on their medication regimen for the duration of this study
- Has the ability to complete bladder diaries, questionnaires, and attend follow-up visits
- Cognitively intact adult and able to understand study procedures and provide informed consent independently.
  - A study team member at the informed consent conversation will assess cognitive ability and the ability to provide informed consent. Assessment will be based on the participant's ability to understand the study procedures and accurately restate their study roles in their own words. No formal cognitive testing will be performed.

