### **Screening Visit:**

Participants may complete informed consent either remotely before the screening visit or in person at the time of screening, depending on preference. Once they have been consented, they will begin the screening visit, which may occur with a routine clinic appointment. At the screening visit a physical exam will occur. If a patient is already having the procedure or exam per standard of care for their clinic visit, we will not repeat the procedure but will instead review the medical record for the results. During this visit, the following will occur:

- medical history and medication review,
- physical examination,
- urinalysis (to assess for hematuria or UTI),
- urine dipstick pregnancy test for women of childbearing potential (the test will be done on the same urinalysis urine sample when possible),

- post-void residual (PRV) volume measurement. This will be conducted by using a non-invasive ultrasound scanner after voluntary voiding to assess for incomplete bladder emptying and rule out urinary retention.
- completion of baseline questionnaires, including the OAB-Q SF 1W and the PGI-S. The OAB-Q SF 1W is a validated 19-item questionnaire that is used to assess patient quality of life. The PGI-S is a single item scale that measures symptom severity. Study questionnaires may be completed on paper or electronically through REDCap, depending on participant preference.

After these screening procedures are done and eligibility is confirmed, the participants will be enrolled in the study. Study-related procedures will only be conducted by clinicians who are members of the study team.

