**Baseline Visit (same day or on a different day):**

- Participants go over the screening results and confirm their enrollment in the study.
- Participants will be instructed that they should remain on stable OAB pharmacotherapy throughout the study.
- They will receive the ZIDA device and get device training based on the ZIDA manufacturer's IFU. They will be instructed to call the study team if, while using the device, they experience any pain, skin irritation, or technical problems.
- They will also be given a 3-day bladder diary and instructions on how to complete it at home over three consecutive days before starting device therapy. This diary records voiding time, urgency, and urgency-urinary-incontinence episodes.
- They will also receive the Device Use Logs, Adverse Event Logs, and Bladder Diaries for the entirety of the study.
- The baseline visit may occur on the same day as the screening visit or may be scheduled for a later date, depending on when all screening procedures are completed and eligibility is confirmed. If all screening assessments are finished during the initial clinic encounter and the participant has enough time to complete the baseline visit, then the baseline visit could be completed. Or, if preferred by the participant, the baseline visit may also be conducted remotely after the screening visit. If this is the case (once eligibility is confirmed) the participant will receive all of the required study materials; the ZIDA device, IFU, conductive gel, and all study logs (Device Use Log, Adverse Event Log, and bladder diaries). Then device training will be conducted either in person or remotely before the participant begins device use. Participants who do not have time to complete all screening and baseline activities in a single visit may return for one additional visit (combined Screening and Baseline visit) to finish any screening procedures and the baseline visit. In all scenarios, the participants will complete all screening procedures, then once they meet eligibility criteria, will receive device training, and receive all study materials before beginning the intervention period.

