## **11.0 Data Management**

All data will be limited to clinical and patient-reported outcomes (e.g., bladder diaries, questionnaires, adverse event logs). Collected data will include demographic information

(age, sex), OAB history, current medications, baseline and follow-up diary metrics, and questionnaire scores. Research data will be coded. Identifiable patient information will be stored in a linking document and stored separately from the research data in a password-protected software accessible only to authorized study staff. All study staff will complete CITI training in human subjects research and will be HIPAA compliant. Only de-identified patient data will be removed from MUSC servers. Hard copy documentation (like consent forms and bladder diaries) will be stored in locked cabinets within MUSC Urology research offices. Any data collected electronically (eg. Electronic consents or questionnaires) will be stored in REDCap. Paper responses will be entered into REDCap by study staff, and hard copies stored as source documentation. If any participants complete electronic consent via REDCap's e-consent module, those signed forms will be stored securely within REDCap under MUSC's encrypted server.

- For this single arm pre/post study design, we plan to enroll a total of 20 participants. Since we expect no more than 20% drop-out, this will yield complete data on at least 16 participants. A sample size of  $n=16$  provides 85% power to detect modest changes (effect sizes of 0.7) in study outcomes, including Total Daily Incontinence episodes). Earlier work by Cava & Orlin (2022) suggest that the device may yield an even larger decline in incontinence episodes (i.e. from  $1.2 \pm 0.8$  at baseline down to  $0.3 \pm 0.3$ , at week 12, corresponding to an effect size of 1.4), meaning that we may likely have even greater statistical power. This sample size would also provide sufficient power (>80%) to detect changes in secondary outcomes, including Quality of Life (OAB-Q SF 1W total score). While primary analysis compares baseline to week 12, repeated-measures models will incorporate interim timepoints (weeks 1, 4, 8) descriptively.

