- Initially, descriptive statistics will be used to characterize the study participants at baseline and at follow-up. Continuous outcomes (i.e. measures of incontinence and quality of life) will be compared pre- and post-use of the device using paired t-tests, or Wilcoxon signed rank tests (if necessary). The proportion of participants who have no incontinence at follow-up will be reported, and these percentages will be compared using McNemar's tests for paired binomial proportions. The results of this study will be vital for helping to design a larger, definitive 2-arm randomized controlled trial.

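### McNemar's test on the proportion with no incontinence has a baseline fixed at 0% by the entry rule, so its p-value only restates the number dry at follow-up

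*Protocol*

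**What the plan says.** The analysis paragraph of Protocol section 11.0 (Data Management) first gives the continuous outcomes, which "will be compared pre- and post-use of the device using paired t-tests" or, if needed, signed rank tests. The next sentence turns to a binary outcome and begins: "The proportion of participants who have no incontinence at follow-up will be reported, and these percentages will be compared using". The method that it then names is "McNemar's tests for paired binomial proportions". It does not say which two percentages are paired.

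Section 5.0 (Inclusion Criteria) limits entry to patients with "Diagnosis of OAB-wet (OAB with urgency urinary incontinence) documented by clinical diagnosis" and sets a baseline minimum of one "UUI episode/day averaged over a 3-day diary".

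Section 10.0 describes a single pre-treatment diary. It is given out at the baseline visit, and participants are to "complete it at home over three consecutive days before starting device therapy". Section 3.0 says that each patient acts as their own control. On size, section 11.0 says "we plan to enroll a total of 20 participants" and expects complete data on at least 16.

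**The concern.** McNemar's test asks whether, among participants who change state, moves from wet to dry and from dry to wet are equally likely. That question has meaning only if both moves are possible. Here the entry rule admits only participants who are wet at baseline, so nobody can move from dry to wet. The baseline percentage is set by eligibility and is not an observed quantity.

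What is at stake is interpretation. A small p-value from this test could be reported as evidence of improved continence, although its comparator is a 0% that the investigators imposed. It also adds nothing for the larger randomized trial that section 11.0 has in view. That trial needs a dry rate and its uncertainty.

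**Working it through.** The protocol gives no figure for this comparison, so there is none to reproduce. Its one power statement concerns effect sizes of 0.7 in study outcomes such as daily incontinence episodes and does not bear on this point.

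**Inputs**
- Enrolled: 20 (sections 6.0 and 11.0). Completers: 20 × (1 − 0.20) = 16 (section 11.0).
- Baseline: a mean of at least 1 UUI episode a day over 3 days, that is, at least 3 recorded episodes (section 5.0).
- Significance level: not stated; 0.05 two-sided is assumed here.

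**Paired table under the entry rule.** Let *b* be the number wet at baseline and dry at follow-up, and *c* the number dry at baseline and wet at follow-up. The baseline dry row is empty, so *c* = 0 and *b* is simply the number dry at follow-up.

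**McNemar with *c* = 0**
- Exact two-sided: p = 2 × 0.5^*b*
- Uncorrected chi-square: (*b* − *c*)²/(*b* + *c*) = *b*, on 1 df
- Continuity-corrected chi-square: (*b* − 1)²/*b*, on 1 df

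| Dry at follow-up (*b*) | Exact p | Uncorrected p | Corrected p |
|---|---|---|---|
| 4 | 0.125 | 0.0455 | 0.134 |
| 5 | 0.0625 | 0.025 | 0.074 |
| 6 | 0.031 | 0.014 | 0.041 |

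The sample size appears in none of these formulas. Six dry participants give p = 0.031 by the exact test whether the denominator is 16 or 20.

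**What the proportion itself conveys** (Clopper-Pearson 95% intervals)
- 6/16 = 37.5%, 15.2% to 64.6%
- 6/20 = 30.0%, 11.9% to 54.3%

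The p-value is the same in both cases; the estimate and its interval are not.

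**Would the test reject if leakage did not change?** Assume that episodes follow a Poisson distribution. The chance of a dry 3-day diary is then exp(−3 × daily rate). At 1 episode a day, the entry minimum, this is exp(−3) = 0.050. With 16 participants each at 5%:
- P(6 or more dry) ≈ 0.00008
- P(4 or more dry) ≈ 0.007, the threshold for the uncorrected chi-square

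A gamma-Poisson model with selection on the baseline diary (assumed mean of 1.2 to 2.0 episodes a day before selection, no treatment effect) gives about 2% to 4% dry by chance. At 4%, the two probabilities are 0.00002 and 0.003.

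If the true rate were 0.5 a day, half the entry minimum, a diary would be dry by chance with probability exp(−1.5) = 0.223. The two probabilities would then be 12.5% and 49%. That requires true leakage well below the qualifying level, and the 49% also requires the uncorrected test, which the protocol does not specify.

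**The case against.** **The comparator is not stated.** Section 11.0 refers to tests in the plural, and diaries are also collected at Weeks 4 and 8. A comparison between two follow-up weeks would not have an empty cell. This stands as a point about the wording. But no week-to-week comparison of dryness is stated anywhere, the sentence just before is explicitly before versus after device use, and each patient is their own control. Baseline is the comparator that the text supports.

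**A dry baseline diary might occur.** In section 10.0, enrolment comes first: "After these screening procedures are done and eligibility is confirmed, the participants will be enrolled in the study". The pre-treatment diary is handed out at the baseline visit. Read literally, someone could be enrolled before the qualifying diary exists and then record no leaks. That participant would breach the inclusion criterion, so this is a reason to reconcile the two sections and does not rescue the test.

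**The harm is limited.** A reader might infer that the analysis will produce a significant result whatever the device does. The documents do not support that: with leakage unchanged, the exact test would almost never reject. A reader might also say that the null is false before treatment begins. Some chance-dry diaries are expected, but too few for the test to detect reliably; the accurate criticism is that the p-value is uninformative. Nor does the plan lack a usable estimate, since the follow-up proportion is to be reported in any case. Natural history and placebo response could make participants dry too, but that limit belongs to any uncontrolled before-after design and applies equally to the paired t-test.

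**Conclusion.** The point holds as a minor error in a supportive analysis. With baseline as the comparator and the entry criterion enforced, the dry-to-wet cell is zero by design, McNemar's null cannot apply, and the p-value is a relabelled count (0.0625 at 5 dry, 0.031 at 6). It should not be presented as a test of improved continence.

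It is no more than that. Dryness is neither the primary endpoint nor among the secondary objectives or endpoints in sections 1.0 and 4.0, no sample-size figure rests on it, and no decision rule is tied to it.

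The structural conclusion rests on the baseline-versus-follow-up reading and on enforcement of the criterion. The false-positive figures also rest on the assumed Poisson and gamma-Poisson models. Because the protocol itself names the test, this is not a detail left to the statistical analysis plan (SAP).

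**What to change.** In section 11.0, delete the McNemar comparison. State instead that the proportion with zero UUI episodes on the Week 12 3-day diary will be reported with an exact (Clopper-Pearson) 95% confidence interval, descriptively and without a hypothesis test. The denominator and the handling of missing Week 12 diaries can be left to the SAP.

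Separately, reconcile the inclusion criteria in section 5.0 with the screening and baseline visits in section 10.0, so that it is clear whether the qualifying diary is completed before eligibility is confirmed.

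The first change costs one sentence and one p-value. Neither the sample size nor the data collected needs to change for it. The second is a clarification; it affects the order of visits only if the sponsor finds that the intended sequence differs from what is written.

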## 12.0 Withdrawal of Subjects

- Participants could be withdrawn from the study if they no longer meet eligibility criteria (like ceasing their medication use or are non-adherent to device use) or for safety concerns (like an adverse reaction).
- Participants can withdraw from the study at any time without penalty by notifying the Principal Investigator or a member of the study team. Data collected up to that point will be retained unless the participant requests their data be removed.
- If a participant withdraws during the study, the reason for withdrawal will be documented in the study enrollment and tracking log maintained by the study team.

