## 4.0 Study Endpoints

- Our primary endpoint is to evaluate the mean change in total daily UUI episodes from baseline to week 12. Exploratory interim analyses at weeks 1, 4, and 8 will be descriptive. Our secondary endpoints include urgency episodes, total voiding frequency per day, QOL questionnaire Overactive Bladder Questionnaire (1-Week Recall) (OAB-Q SF 1W), Patient Global Impression of Improvement (PGI-I) responder, and any adverse events.
- Device usability and satisfaction will be measured at Week 12 using the Usability & Satisfaction Survey. This survey is a six-item questionnaire adapted from prior OAB studies. Five items are rated on a five-point Likert scale (1 = Strongly disagree to 5 = Strongly agree) to measure device ease of use, comfort, clearness of instructions, convenience, and patient willingness to continue therapy. There is also an open-ended feedback question. We'll summarize responses to get a sense of usability and patient experience.
- Adherence will be measured as the proportion of prescribed weekly sessions completed, based on the participant's Device Use Log. Study staff will review logs during remote check-ins (Weeks 1, 4, 8, and 12). Adherence will be expressed as both total number and percentage of completed sessions (out of 12).
- Safety related to usability will also be captured through the Adverse Event Log, reviewed by the principal investigator at each contact.

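### Section 12.0 lets staff withdraw participants from the study for device non-adherence or for ceasing medication, with no Week 12 diary afterwards, which opens the primary pre-post result to selective loss

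*Protocol*

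**What the plan says.** Section 12.0 (Withdrawal of Subjects) says that staff may withdraw participants from the study "if they no longer meet eligibility criteria (like ceasing their medication use or are non-adherent to device use"). Safety concerns are listed as a further reason. The rule is discretionary, gives no threshold for non-adherence, and acts on study participation as a whole. On data, the section says "Data collected up to that point will be retained unless the participant requests their data be removed"; that sentence stands in the bullet on voluntary withdrawal. It adds that "the reason for withdrawal will be documented in the study enrollment and tracking log maintained by the study team". Neither this section nor Section 10.0 schedules a diary or final visit for a participant who has been withdrawn.

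The eligibility lists in Section 5.0 contain a medication criterion (stable treatment for at least 4 weeks, with intent to continue) but none on device adherence. In Section 4.0 adherence is an outcome: "Adherence will be measured as the proportion of prescribed weekly sessions completed", given as a number and a percentage out of 12.

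The primary endpoint in Section 4.0 is the mean change in daily UUI episodes from baseline to Week 12. Section 11.0 tests it with a paired t-test or Wilcoxon signed rank test, compares the proportion without incontinence by McNemar's test, and gives the interim timepoints a descriptive role. On sample size it says "we plan to enroll a total of 20 participants" and then: "Since we expect no more than 20% drop-out, this will yield complete data on at least 16 participants".

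**The concern.** A participant who misses sessions or stops medication may be doing so because of how symptoms have responded. If staff then end that person's participation, no Week 12 value exists and the paired comparison cannot use the person. The choice of who contributes to the primary mean is then partly made after treatment starts, by unblinded staff, with no stated threshold. A single-arm study has no comparison group in which similar losses would occur.

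The rule also sits badly with the rest of the protocol. It treats non-adherence as a failure of eligibility although no such criterion exists, and it lets staff cut short the behaviour that the adherence endpoint is meant to measure.

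At stake are the mean change, the proportion without incontinence and the adherence figure. Section 11.0 says the results are to help design a randomized trial, so a distorted estimate would carry into that trial's planning.

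**Working it through.** **Inputs.** From Section 11.0: 20 enrolled, at most 20% drop-out, 16 with complete data, effect size 0.7, power 85%, and the earlier device result of 1.2 falling to 0.3 episodes/day, a fall of 0.9. Assumed, because the protocol does not state it: alpha 0.05.

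**1. The plan's own figures.** 20 × (1 − 0.20) = 16, as stated. The protocol says that n = 16 "provides 85% power to detect modest changes (effect sizes of 0.7) in study outcomes". For a paired t-test with 15 degrees of freedom and noncentrality 0.7 × √16 = 2.8, power is 84.7% one-sided and 74.5% two-sided. The stated 85% therefore reproduces as a one-sided 0.05 test on 16 people with both diaries. The sidedness is a separate matter; what counts here is that the calculation rests on 16 complete pairs out of 20.

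**2. Effect of losing 4 of 20.** Let D be the mean change in the 16 who remain, and let the 4 removed have mean change r × D. Then:

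- 20-person mean = (16D + 4rD)/20 = D(0.8 + 0.2r)
- overstatement by the 16-person mean = 1/(0.8 + 0.2r) − 1

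| r (assumed) | 0.8 + 0.2r | Overstatement |
|---|---|---|
| 1.00 | 1.00 | 0% |
| 0.50 | 0.90 | 11% |
| 0.25 | 0.85 | 18% |
| 0 | 0.80 | 25% |

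At r = 0, a fall of 0.90 episodes/day in 16 is 16 × 0.90/20 = 0.72 over all 20, and an effect size of 0.70 becomes 16 × 0.70/20 = 0.56. If r exceeds 1 the sign reverses: at r = 1.5, 1/1.1 − 1 = −9%.

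**3. Fewer losses under this rule.** The 20% covers drop-out for any reason. With k people removed, everyone else observed and r = 0, the overstatement is 20/(20 − k) − 1: 5% for k = 1, 11% for k = 2, 18% for k = 3.

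**4. Power if all 20 are followed.** At a uniform effect size of 0.7, power is 91.5% one-sided or 84.3% two-sided. If the 4 retained people respond less (SD of change 1 in everyone, 100,000 simulated trials), two-sided power is about 76% when their mean is 0.35 and 63% when it is 0, against 74.5% for 16 completers. Full follow-up removes the selection but does not guarantee more power.

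**The case against.** Much can be said for the protocol. Withdrawal is permitted, not required, and reasons are logged, so losses under this rule can be identified. The drop-out ceiling covers safety, voluntary withdrawal and loss to follow-up as well, so attributing all 4 losses to this rule is an extreme case. Repeated-measures models using the interim diaries could partly address loss that depends on earlier observed change. The study question concerns add-on use with stable medication, so whether people who stop medication belong in the primary mean is a choice of estimand. These points stand. They limit the size and certainty of the problem, but they do not supply the missing Week 12 diaries, and the protocol gives the interim data only a descriptive role.

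A reader might infer more than the text supports:

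- *That the plan prescribes a completer analysis.* It names no analysis set, which may be left to the SAP. The consequence here follows from a paired test and a missing Week 12 value.
- *That those removed are non-responders.* This is not documented. Someone may stop medication after improving, or because of cost or side effects, both named in Section 2.0, and sessions may be missed for convenience.
- *That a responder falling below one UUI episode/day becomes ineligible.* The criterion is fixed at baseline, so later improvement cannot breach it.
- *That the withdrawn vanish from the adherence result.* With 16 people at 11/12 and 4 withdrawn at 4/12, leaving the 4 out would give 92% instead of (16 × 11 + 4 × 4)/240 = 80%. But adherence is defined out of 12 and nothing excludes the withdrawn. The narrower fault is that their handling is unstated and withdrawal itself stops further sessions, so the bias could run either way.
- *That any change of medication triggers withdrawal.* The example given is ceasing medication only.

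**Conclusion.** The point holds as a fault in the withdrawal rule. Section 12.0 permits study-level removal for conduct that may depend on response, makes no provision for a Week 12 diary afterwards, and labels non-adherence an eligibility failure that Section 5.0 does not contain. Because the primary comparison needs a Week 12 value, following the rule as written allows selective loss that no later analysis plan can undo, and the single-arm design offers nothing to offset it.

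The size is an assumed range: 0% to 25% overstatement of the mean change. It rests on all 4 allowed losses coming from this rule and on their response lying between that of the completers and none at all. It is neither an estimate of what will happen nor proof of direction. The matter should be corrected, given how little the correction costs in a 20-person study meant to inform a randomized trial.

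**What to change.** Amend Section 12.0 to separate stopping the device or medication from leaving the study:

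- State that non-adherence or ceasing medication is not by itself a reason for study withdrawal.
- Continue the remaining scheduled diaries and the Week 12 visit for all who agree.
- Analyse all participants with a Week 12 diary, whatever their adherence.
- Record medication cessation and its date, so that results can be shown with and without those participants. Which of the two is primary is an estimand choice for the sponsor.
- Report adherence out of 12 for everyone given a device, including those who stop early.
- Reconcile the eligibility wording in Section 12.0 with the criteria in Section 5.0.

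The cost is amendment wording, a few extra diaries and final visits, and possibly a smaller estimated effect. Withdrawal for safety or at the participant's request is untouched, and no clinical stopping rule is proposed or changed.
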